### Clinical/Symptom Measures

- Structured Clinical Interview for the DSM-IV (SCID-IV) – (*screening*)
- Symptom rating scales: Young Mania Rating Scale (YMRS); Hamilton Rating Scale for Depression (HRSD); Brief Psychiatric Rating Scale (BPRS) – (*all visits*)
- Smoking questionnaire – (*screening, baseline, week 6, week 12*)

|   |   |  |
|---|---|--|
|  | Protocol Title:                           | 1/2-Pramipexole in Bipolar Disorder: Targeting Cognition (PRAM-BD) |
|   | Principal Investigator Name/Contact Info: | [name]   |
|   | Primary Contact Name/Contact Info:        | [name]
[contact]                          |
|   | Date Revised:                             | March 23, 2016 – date of IRB approval May 6, 2017                  |
|   | Study Number:                             | GCO 13-0237, HS 14-00328   |

Neurocognitive/Functional Measures

- Screening cognitive battery (see inclusion criteria 4.) – (*screening*)
- Cognitive assessment: MATRICS Consensus Cognitive Battery (MCCB- plus; see description below) – (*baseline, week 6, week 12*)
- The Probabilistic Stimulus Selection Task – (*baseline, week 6, week 12*)
- UCSD Performance Skills Assessment (UPSA) – (*baseline, week 12*)
- The World Health Organization Disability Assessment Schedule (WHODAS 2.0) – (*baseline, week 12*)

| The MATRICS Consensus Cognitive Battery | Domain               | Note/Description               |
|---|-----------------------------|---------------------------------------|
| Category Fluency                                      | Speed of Processing         | Total animals in 60 seconds           |
| BACS Symbol Coding                                    | Speed of Processing         | Matching numbers to symbols           |
| Trail Making Test Part A                              | Speed of Processing         | Dot-to-dot: Numbers only              |
| CPT-Identical Pairs                                   | Attention/Vigilance         | Computerized numeric stimuli          |
| Letter-Number Span                                    | Working Memory              | Recoding numbers and letters in order |
| WMS-III Spatial Span                                  | Working Memory              | Visual sequence forward and backward  |
| Hopkins Verbal Learning (HVLT)                        | Verbal Learning             | 12 word list x 3                      |

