| Brief Visuospatial Memory Test (BVMT)                 | Visual Learning             | 6 designs to be drawn from recall     |
| NAB Mazes   | Reasoning & Problem Solving | Pencil-paper maze solutions           |
| MSCEIT Managing Emotions                              | Social Cognition            | Situational social judgments          |
| Additional Measures (“Plus”)            | ---                         | ---                                   |
| Affective Go-no-go                                    | Affective Neuroscience      | Emotional modulation of inhibition    |
| Emotional Stroop                                      | Affective Neuroscience      | Affective Bias/Cognitive Control      |

|   |   |  |
|---|---|--|
|  | Protocol Title:                           | 1/2-Pramipexole in Bipolar Disorder: Targeting Cognition (PRAM-BD) |
|   | Principal Investigator Name/Contact Info: | [name]   |
|   | Primary Contact Name/Contact Info:        | [name]
[contact]                          |
|   | Date Revised:                             | March 23, 2016 – date of IRB approval May 6, 2017                  |
|   | Study Number:                             | GCO 13-0237, HS 14-00328   |

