**Primary hypothesis testing:** 100 participants will be randomized in a 1:1 allocation to treatment with pramipexole or placebo. The primary assessment of safety will be based on the incident of adverse event rates and standardized mood ratings at each visit. Differences in the incidence of individual adverse events will be compared between randomization arms using Poisson regression. Exact 95% confidence intervals (based on the Poisson distribution) for the risk ratios for individual adverse events for treatment with pramipexole versus placebo will be computed and may incorporate an estimated overdispersion parameter if observed variability exceeds that determined by the Poisson distribution. Performance on the IGT will also be used to track potential changes in impulse-control (baseline, weeks 6 and 12). We will test for correlations between IGT performance and mania symptoms at the times of testing (simultaneous measurements). Moreover, we will use IGT change scores as predictors in regression models to evaluate changes in mania ratings at concurrent time points as well as future time points. This will directly address the question of whether or not changes in IGT strategy serve as markers of current mania and/or impending affective destabilization.

The relative specificity of pramipexole in binding to D2/D3 receptors allows for a unique opportunity to enhance DA in neural networks associated with specific aspects of cognition as well a reward processing, which will be carefully assayed in this study so that exploratory analyses will be able to test questions related to the role for these receptors across several interacting domains in BD, at least at the level of behavior. Exploratory analyses will include specific domains and individual tasks which will be modeled to account for main effects and interactions (as described in primary analyses below).

The primary outcome for efficacy is change in cognition from baseline to week 6 (MCCB Composite). The null hypothesis is that there is no difference in this change between

|   |   |  |
|---|---|--|
|  | Protocol Title:                           | 1/2-Pramipexole in Bipolar Disorder: Targeting Cognition (PRAM-BD) |
|   | Principal Investigator Name/Contact Info: | [name]   |
|   | Primary Contact Name/Contact Info:        | [name]
[contact]                          |
|   | Date Revised:                             | March 23, 2016 – date of IRB approval May 6, 2017                  |

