|   | Study Number:                             | GCO 13-0237, HS 14-00328   |

patients on pramipexole vs. patients on placebo. This will be tested in an intent-to-treat analysis using a 0.05 level two-tailed test based on a mixed effects regression model, with patients considered to be a random effect, and randomization group a fixed effect. In order to preserve statistical power, change in MCCB Composite will be used as the dependent variable; however, secondary analyses will be conducted for MCCB domain scores and measure of reward processing. The use of two post baseline evaluations (weeks 6 and 12) and the ability of the model to incorporate all available data, also improves efficiency (i.e., power). This approach will also be employed in subsequent comparisons of specific domains and for measures of reward processing. These additional analyses will be conducted at a nominal 0.05 level and will focus on enhancing interpretation of the primary analysis by highlighting the specific domains most affected by pramipexole. Since randomization is stratified by concomitant antipsychotic use and baseline depression status, indicators of stratification will be included in the model as fixed effects.

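### Separate 0.05 tests in seven MCCB domains cannot show which domains pramipexole affects most, and no treatment-by-domain test is specified

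*Combined protocol and SAP*

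**What the plan says.** Section 5(h), Statistical Methods, names one primary efficacy outcome: change in the MCCB Composite from baseline to week 6, tested two-tailed at 0.05. The model is described "with patients considered to be a random effect, and randomization group a fixed effect", with the stratification factors added as fixed effects. No interaction is listed.

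The same text then adds that "secondary analyses will be conducted for MCCB domain scores and measure of reward processing". On method: "This approach will also be employed in subsequent comparisons of specific domains and for measures of reward processing". On error level: "These additional analyses will be conducted at a nominal 0.05 level". On purpose, they "will focus on enhancing interpretation of the primary analysis by highlighting the specific domains most affected by pramipexole".

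Earlier in the same section the domain analyses carry a different label: "Exploratory analyses will include specific domains and individual tasks which will be modeled to account for main effects and interactions". That sentence refers the reader to the primary analyses described further down for the detail. The Exploratory Aim in section 1 also speaks of main and interactive effects across cognition, affect and reward, without giving a model.

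The MCCB table in section 5(f) lists seven domains: speed of processing, attention/vigilance, working memory, verbal learning, visual learning, reasoning and problem solving, and social cognition ("MSCEIT Managing Emotions"). The reward measure is "The Probabilistic Stimulus Selection Task".

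**The concern.** The stated goal is to rank or single out domains. The stated method fits the composite model to one outcome at a time. A model for a single domain has no domain factor, so it cannot estimate how the treatment effect differs between domains. A significant result in one domain and a non-significant result in another is not evidence that the two effects differ.

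Section 5(h) ties the domain analyses to the mechanistic question of whether D2/D3 agonism acts on specific aspects of cognition. If pramipexole helps all domains equally, the plan as written would still tend to produce a list of affected and unaffected domains, and would overstate the effect in the domain that comes out on top.

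This is only partly a multiplicity problem. Adjusting the seven p values limits false findings when there is no effect. It does nothing for the uniform-effect case, because the contrast that is needed is never estimated.

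**Working it through.** **Inputs from the documents.** 100 patients randomized 1:1, so 50 per arm; composite d about 0.55; about 80% power; two-tailed 0.05 (section 5(h), Sample size/Power). Seven domains (section 5(f)). Nominal 0.05 per domain.

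**Assumed input.** A common correlation r between domain change scores. The documents give none, so r runs from 0.1 to 0.8. Equal variances and a normal approximation are also assumed.

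**1. The plan's own figure.** The standard error of an observed d is √(2/50) = 0.20. For d = 0.55 the mean of z is 0.55/0.20 = 2.75, and power is Φ(2.75 − 1.96) = 78.5%. The detectable d at 80% power is 0.56. The stated 80% is reproduced to rounding.

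**2. Domain effect under a uniform effect.** If the composite is the mean of seven equally correlated domains and has d = 0.55, each domain has d = 0.55 × √((1 + 6r)/7). At r = 0.3 this is 0.55 × √(2.8/7) = 0.348. Power per domain is then Φ(0.348/0.20 − 1.96) = Φ(−0.22) = 41%, so on average 7 × 0.41 = 2.9 of the seven domains are significant although all benefit equally.

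**3. How often a partial pattern appears.** By simulation (400,000 draws per setting), the percentage of trials is:

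| Setting | r = 0.1 | 0.3 | 0.5 | 0.7 | 0.8 |
|---|---|---|---|---|---|
| Uniform effect, composite d = 0.55: some but not all domains p < 0.05 | 83 | 85 | 75 | 54 | 42 |
| The same, among trials with a significant composite | 93 | 94 | 80 | 54 | 40 |
| Uniform effect, every domain d = 0.55: some but not all | 77 | 66 | 56 | 43 | 35 |
| No effect: at least one domain p < 0.05 | 30 | 27 | 23 | 18 | 15 |
| No effect: significant composite and a partial pattern | 4 | 5 | 5 | 5 | 4 |

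For seven independent tests with no effect, the exact figure is 1 − 0.95⁷ = 30.2%. Adding one reward measure with the same assumed effect raises the unconditional figures (the first, third and fourth rows) by about 1 to 5 points.

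**4. Overstatement of the leading domain.** The expected largest of seven equally correlated estimates is d + 0.20 × √(1 − r) × 1.352, where 1.352 is the expected maximum of seven standard normals. At r = 0.3: 0.348 + 0.20 × 0.837 × 1.352 = 0.57, against a true 0.35.

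**5. The missing test.** A 6-df group-by-domain test at 0.05 rejects in about 5% of trials under no effect or a uniform effect, at every r tried (0 to 0.7).

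**6. Power of that test.** Take one domain at d = 0.55 and six at 0.20. On the z scale these are 2.75 and 1.00, a gap of 1.75. The noncentrality is 1.75² × (6/7)/(1 − r) = 2.625/(1 − r), that is 2.9, 3.75 and 5.25 at r = 0.1, 0.3 and 0.5. The power is about 20%, 25% and 35%.

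**The case against.** The plan already limits these analyses. It has one primary outcome, calls the domain tests secondary or exploratory, calls their level nominal, and gives them the role of helping to interpret the composite. Unadjusted tests openly labelled in this way are common. This stands as far as multiplicity goes, and it is why Holm adjustment is not required here. It does not answer the uniform-effect case, since a nominal label does not turn separate tests into a between-domain comparison.

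The plan states no rule that a domain is highlighted when p < 0.05, so counting significant domains is this review's stand-in for how the results would be read. That is fair. Highlighting by effect size instead would have the same gap, and step 4 shows the overstatement it carries.

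Three stronger readings are tempting and should be resisted.

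- A reader might infer that a drug with no effect will often be reported as domain-specific. The 15% to 30% applies only if domains are read whatever the composite shows. If they are read only after a significant composite, a partial pattern occurs in about 4% to 5% of trials. The plan does not state that sequence, but its wording on interpretation is compatible with it.
- A reader might count two tests per domain, at weeks 6 and 12, and so 14 in all. The plan describes one mixed model per outcome using both visits, and lists no separate domain test at each visit.
- A reader might say that the plan rules out an interaction test. It mentions interactions twice. The accurate statement is that none is specified and that the cross-reference leads to a model without one.

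**Conclusion.** The concern holds for the domain analyses. Separate group tests at 0.05 cannot support a statement about which domains are affected most, and the plan specifies no test that can. With 50 per arm and a truly uniform effect giving composite d = 0.55, a partial pattern appears in about 83% to 86% of trials at r = 0.1 to 0.3, 75% at 0.5, 54% at 0.7 and 42% at 0.8. A partial pattern is therefore the usual result only up to an r of about 0.7, and r is an assumption the documents do not settle.

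The primary composite test, its type I error and the sample size are untouched. The change should be made before analysis, because domain specificity is a stated scientific output of the trial.

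**What to change.** Add to the statistical methods in section 5(h) one mixed model of the seven domain T-score changes at week 6, with group, domain and group-by-domain (6 df), an unstructured covariance across domains within patient, and the stratification factors. The domain scores already share the MCCB T-score scale, so a uniform effect here means an equal difference in T-score points.

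Report the group-by-domain test and show all seven group differences with 95% CIs side by side. State that no domain will be described as more affected than another on separate p values alone, and that without support from the interaction test domain differences are descriptive. Either define the interactions now mentioned or remove the cross-reference. Label the domain, task and reward analyses as exploratory in both places. Holm adjustment for single-domain claims is optional.

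The cost is some wording and one extra model; no new data, visits or patients are needed. The drawback is the limited power in step 6, about 20% to 35% in that example. The plan should therefore also say that a non-significant interaction test is not proof of a uniform effect.

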## f) Procedures Involved in the Human Research

All eligible participants will undergo study visits at screening, baseline (week 0), week 1, week 2, week 3, week 4, week 6, week 8, and week 12, (end of study).

Randomization will be conducted via a computer generated program and all study staff will be blinded unless un-blinding is required for safety reasons. Subjects will be randomized on a 1:1 ratio with stratification for concomitant antipsychotic status and depression at baseline (HRSD <8 vs  $\geq$  8). Study drug will be blinded and matched to placebo. Adapting from our previous work in BD and according to package labeling, the dosage titration schedule will be slow and flexible. Dosing will be initiated at 0.25 mg QHS on night one, followed by 0.25 mg BID day two onward, and increased every week to a target of 4.5 mg/day. As compared with our previous maximum 1.5 mg/day ([name] et al. 2012), we opted to allow up to 4.5 mg/day (the maximum approved dosage in Parkinson’s disease) to ensure adequate target engagement. We are familiar with this dose range, as 4.5 mg/day was allowed in our study in BD depression (Goldberg et al. 2004). Dosing will be flexible based on side effects; however, if 1.5 mg/day cannot be tolerated, the subject will be discontinued. Titration will occur up to week 6 and then efforts will be made to maintain the same dose until the completion of the trial (week 12).

Measures are described in detail below:

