*Missing data:* Although the mixed effects modeling approach allows patients with evaluations at week 4 but missing at week 8 to be included, bias may be introduced if missing data are related to patient response. For example, it may be that patients responding poorly are less likely to have a week 8 evaluation than those patients with better response. The mixed effects analysis would weigh the results of these poorly performing patients less (as they provide fewer data) and in the presence of a positive effect of pramipexole, decrease power. To assess the extent that any bias has been introduced by missing data, we will impute missing week 8 values. Note that if no bias is produced by the missing data, analyses with and without imputation should provide virtually identical results. If the analyses produce different results, we will work to identify the causes by comparing patients with and without missing data. Based on our prior trial experience we expect relatively few patients (< 10) to be missing the week-8 visit due to attrition. Patients with missing data will have their 8 week MCCB score imputed via multiple imputation assuming that the data are MAR, i.e., the missing nature of the variable is independent of the value of the variable given the observed data. The specific imputation model to be used will be determined prior to examination of any outcome data, but will include MCCB score at baseline and at 4 weeks. Separate imputations will be done for each randomization group.

*Due to the 12 week course of the study, mixed models will still be utilized for variables collected with sufficient frequency; however, when incorporating missing data, we will only be able to do so when at least two time points are included. Subjects with only baseline data will be included in descriptive analyses but will be dropped for analyses where necessary.*

|   |   |  |
|---|---|--|
|  | Protocol Title:                           | 1/2-Pramipexole in Bipolar Disorder: Targeting Cognition (PRAM-BD) |
|   | Principal Investigator Name/Contact Info: | [name]   |
|   | Primary Contact Name/Contact Info         | [name]
[contact]                          |
|   | Date Revised:                             | March 23, 2016 – date of IRB approval May 6, 2017                  |
|   | Study Number:                             | GCO 13-0237, HS 14-00328   |

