**Sample size/Power:** A total of one hundred patients will be randomized 1:1 (50 from ISMMS, 50 from ZHH). The adequacy of this sample size is based on the ability to reject the null hypotheses of no difference between treatment groups with respect to the MCCB composite score with sufficient power (80%). Ideally, sample size would be determined to ensure adequate power to detect the minimal clinically important difference. No specific guidelines exist to establish such a threshold in this setting but cognitive change of at least a moderate effect would likely be necessary to allow for clinical meaningfulness. Our sample size provides approximately 80% power to detect a standardized difference (e.g., Cohen’s d) of approximately 0.55 with a two-tailed 0.05 level test. For the pre-specified subgroup analysis based on concomitant use at baseline, the detectable standardized difference is about 0.80.

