## 6) Risks to Subjects

During the informed consent process, participants will be informed of the potential risks associated with the study. At each weekly visit the study physician will meet with participants and conduct a thorough review of symptoms including mood, and suicidal ideation. If there is an acute worsening of symptoms the study clinicians will review the case with the PI (or will make an emergency decision as needed) to ensure that the participant receives emergency care or hospitalization. Participation in the study will be discontinued in any case of clear symptom worsening. Between weekly visits, the participants will have emergency contact information.

Along with closely monitoring for symptom exacerbation, each visit with the study physician will entail a detailed side effect evaluation, which will include vital signs and a

|   |   |  |
|---|---|--|
|  | Protocol Title:                           | 1/2-Pramipexole in Bipolar Disorder: Targeting Cognition (PRAM-BD) |
|   | Principal Investigator Name/Contact Info: | [name]   |
|   | Primary Contact Name/Contact Info:        | [name]
[contact]                          |
|   | Date Revised:                             | March 23, 2016 – date of IRB approval May 6, 2017                  |
|   | Study Number:                             | GCO 13-0237, HS 14-00328   |

side effect checklist. The most common side effects of pramipexole are nausea, headache, dizziness, insomnia, constipation, muscle weakness, abnormal dreams, confusion, memory problems, urinary frequency. Participants will be educated about the potential for these side effects. Rare side effects have also been reported including sedating effects, impulse control symptoms (e.g. gambling), hallucinations, and orthostatic hypotension. The informed consent process will alert participants to these potential risks and close monitoring will ensure prompt response to any adverse effects with appropriate treatment and/or study discontinuation, as indicated.

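### Drop-out driven by the discontinuation rules can bias the week 6 comparison toward either arm, and the imputation is not required to use the recorded reasons for withdrawal

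*Combined protocol and SAP*

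**What the plan says.** The Missing data paragraph (section 5(h), Statistical Methods) first says, without giving a direction, that missingness related to response may cause bias. Its example is that poor responders leave, the mixed model gives them less weight, and this would, "in the presence of a positive effect of pramipexole, decrease power". Missing scores are then multiply imputed under MAR, separately by arm. The imputation model is to be settled before any outcome data are examined, "but will include MCCB score at baseline and at 4 weeks"; no other variable is required. The plan reasons that if missing data cause no bias, results with and without imputation should be almost the same. It expects fewer than 10 patients to be missing through attrition and does not split them by arm. A closing note says that missing data can be handled only where there are at least two time points, and that patients with only baseline data may be dropped from analyses.

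Other sections determine who leaves. Section 5(f) says of the dose titration, which runs up to week 6, that "if 1.5 mg/day cannot be tolerated, the subject will be discontinued". Section 5(j) discontinues patients who reach YMRS or HRSD thresholds or are at risk of suicidal behavior. Section 6 discontinues for clear symptom worsening and allows discontinuation for adverse effects; its list of the drug's most common side effects includes "abnormal dreams, confusion, memory problems, urinary frequency". The side-effect checklist, YMRS and HRSD are taken at all visits, and the MCCB at baseline, week 6 and week 12 (section 5(f)).

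**The concern.** The example covers one mechanism: poor response leads to drop-out in the same way in both arms. The discontinuation rules allow others. Intolerance of the active drug should fall mainly on the pramipexole arm. Because the listed side effects include cognitive ones, some of those stopped could be patients whose cognition has worsened on the drug. If they leave before week 6, the remaining pramipexole patients look better than the arm as randomized. Mood-related withdrawals could fall more on either arm.

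Much of this drop-out would be predictable from data the trial already holds. MAR can be a reasonable assumption given the checklist and mood ratings, and still fail given MCCB scores alone. A patient stopped during titration may have only a baseline MCCB, so imputation would in effect copy the patients in that arm who stayed. The planned comparison with and without imputation could then show close agreement while both results carry the same bias.

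**Working it through.** **Inputs from the plan.** "100 participants will be randomized in a 1:1 allocation to treatment with pramipexole or placebo", so 50 per arm. The primary comparison is change in MCCB Composite from baseline to week 6, "using a 0.05 level two-tailed test based on a mixed effects regression model". The sample size is said to give "approximately 80% power to detect a standardized difference" "of approximately 0.55 with a two-tailed 0.05 level test". Fewer than 10 patients are expected to be missing.

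**Step 1: the plan's own figure.** The standard error of the standardized difference is sqrt(2/50) = 0.20. Power = Φ(0.55/0.20 − 1.96) = Φ(0.79) = 78.5% (77.7% by the noncentral t). The detectable difference at 80% is 0.20 × (1.960 + 0.842) = 0.56. The stated figure reproduces approximately.

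**Step 2: bias under no true effect.** Assume m patients are missing, all on pramipexole, and that they lie D SD of MCCB change below those who stay. The mean of those who stay exceeds the full-arm mean by b = (m/50) × D. With SE = sqrt(1/(50 − m) + 1/50), the two-sided rejection rate is 1 − Φ(1.96 − b/SE) + Φ(−1.96 − b/SE). For m = 9 and D = 1.0: b = 0.18, SE = 0.211, b/SE = 0.854, and the rate is 0.1344 + 0.0025 = 13.7%.

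| m missing, all on pramipexole | D (SD) | Bias toward drug (SD) | Type I error |
|---|---|---|---|
| 3 | 0.5 | 0.03 | 5.3% |
| 3 | 1.0 | 0.06 | 6.0% |
| 5 | 0.5 | 0.05 | 5.7% |
| 5 | 1.0 | 0.10 | 7.8% |
| 9 | 0.5 | 0.09 | 7.1% |
| 9 | 1.0 | 0.18 | 13.7% |

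The same losses placed on placebo would give the same bias against the drug.

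**Step 3: would the planned check reveal it?** This was simulated with 3,000 runs and 50 per arm. MCCB change has an assumed correlation r with a recorded trigger score. Nine pramipexole patients are lost, with higher trigger scores more likely to go. Imputation is by arm, with 10 imputations. True effect is zero.

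| r | Observed data: bias, error | Imputation without trigger | Imputation with trigger |
|---|---|---|---|
| −0.3 | 0.07 SD, 6.2% | 0.07 SD, 6.1% | 0.00 SD, 4.9% |
| −0.5 | 0.11 SD, 8.3% | 0.11 SD, 8.0% | 0.00 SD, 4.8% |
| −0.7 | 0.16 SD, 11.9% | 0.16 SD, 11.8% | 0.00 SD, 4.7% |

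The first two results agree closely in every row, and both are biased. With 7 lost on pramipexole and 2 on placebo (r = −0.5), the bias is about 0.05 SD without the trigger and about −0.01 SD with it. If instead the 9 highest trigger scores are all removed, their mean is about 0.2625/0.18 = 1.46 SD, so the mean of those who stay is −1.46 × 9/41 = −0.32, and r = −0.5 gives a bias of about 0.16 SD.

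Two features of the simulation matter. Drop-out depends only on the recorded trigger, so the success of the last column partly follows from the set-up. The baseline score was generated independently of both change and trigger, so it could not help the imputation.

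**Step 4: direction with a true effect of 0.55.**

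- Poor responders leave either arm (9 missing): the estimate falls to 0.47, and power falls from 76% with complete data to 66%. The plan's example is right for its own mechanism.
- All 9 losses fall on pramipexole through the trigger (r = −0.5): the estimate rises to 0.67, and the rejection rate rises from 79% to 89%.

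**Step 5: who is covered.** A patient stopped before week 6 without an exit MCCB has one MCCB time point. The two-time-point rule then allows that patient to be dropped. The paragraph also refers to week 4 and week 8 scores, whereas the MCCB is scheduled at weeks 6 and 12, so imputation of the week 6 primary endpoint is not actually specified.

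**The case against.** A reader might infer that the plan claims drop-out makes its test conservative. It does not. It acknowledges bias in general terms, and the power remark is one example, conditional on a true benefit. The null calculations above do not contradict that remark.

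The required MCCB scores are a minimum. The imputation model is still open and could take in the triggers, so it is not shown that the final analysis will condition on the wrong variables. Nor is their absence from the primary mixed model a defect: adjusting for mood ratings or side effects after randomization would adjust for consequences of treatment.

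The mechanism can also run the other way. Section 6 lists ten common side effects without frequencies, and only two are plainly cognitive; stopping for nausea implies no MCCB deficit. The Background reports evidence that pramipexole may be an effective adjunctive antidepressant in bipolar disorder, so depressive withdrawals could fall more on placebo. Section 5(e) allows an end-of-study MCCB. If that covers early exit, the problem shrinks, but section 5(j) names only safety measures and a follow-up contact at termination.

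All of this limits the size and certainty of the bias. It does not rescue the planned check, which can show agreement whether or not bias is present. Nor does it bring in patients who may be dropped for having only a baseline score.

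**Conclusion.** The point holds in a limited form. The plan recognizes possible bias, but it illustrates only lost power, requires only MCCB scores for imputation, and relies on a comparison that cannot detect drop-out driven by recorded triggers. The bias may favour either arm. With fewer than 10 missing, a plausible range toward pramipexole is about 0.03 to 0.18 SD, against a design effect of 0.55, with type I error of about 5% to 14%. It is near 0.05 SD for a 7 versus 2 split at r = −0.5. The arm split, the outcome gap D and the correlation r are assumptions; the documents give none of them.

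A reader might go further and infer a large bias in the drug's favour: 20% of the pramipexole arm lost, none on placebo, and those lost 1.0 SD below the arm average would give 0.20 × 1.0/0.80 = 0.25 SD and about 21% error. The documents do not support that case. It needs 10 losses in one arm, more than the plan expects in total, and nothing in the documents shows that drop-out would be so one-sided. The issue deserves correction because the remedy is cheap, not because a false positive is likely.

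**What to change.** Four changes to the Missing data paragraph, made before outcome data are examined:

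1. State that drop-out may bias the comparison toward either arm, and that agreement with an MAR imputation based on MCCB scores alone is not evidence of no bias.
2. Require a few auxiliary variables in the within-arm imputation model: last HRSD, last YMRS, a side-effect checklist summary (or its cognitive items, if it has them; the documents do not list the items) and last dose level reached. Keep these post-randomization variables out of the primary mixed model.
3. Apply the imputation to the week 6 primary MCCB, and include randomized patients whose only MCCB is at baseline instead of dropping them.
4. Report withdrawals before week 6 by arm and reason beside the primary result.

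The cost is SAP text and a somewhat larger imputation model. With about 50 per arm the auxiliaries must stay few, and honest imputation costs power: in the Step 4 pramipexole-loss case, imputation with the trigger rejected in 72% of runs, against 79% with complete data. Patients removed at a threshold have few counterparts still on study, so the model extrapolates for them, and the plan should say so. No new assessments are needed, and no change to any dosing or stopping rule is proposed.
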